1.5. Compliance Statement

This study will be conducted in full accordance with all applicable Children's Hospital of Philadelphia Research Policies and Procedures and all applicable Federal and state laws and regulations including 45 CFR 46, 21 CFR Parts 50, 54, 56, 312, 314 and 812 and the Good Clinical Practice: Consolidated Guideline approved by the International Conference on Harmonization (ICH). Any episode of noncompliance will be documented.

The investigators will perform the study in accordance with this protocol, will obtain consent and assent, and will report adverse events in accordance with The Children's Hospital of Philadelphia IRB Policies and Procedures and all federal requirements. Collection, recording, and reporting of data will be accurate and will ensure the privacy, health, and welfare of research subjects during and after the study.

2. Study Objectives

Congenital hyperinsulinism due to mutations in the K_{ATP} channel ($K_{ATP}HI$) is characterized by severe hypoglycemia unresponsive to available medical therapy. Currently, most patients require a pancreatectomy to control the hypoglycemia, leading to prolonged hospitalization and life-threatening complications. Our pre-clinical studies demonstrate that antagonism of the glucagon-like peptide-1 receptor (GLP-1r) by exendin-(9-39) suppresses insulin secretion and corrects fasting hypoglycemia in mice lacking K_{ATP} channels (*SUR-1^{-/-}* mice). Preliminary results from a clinical pilot study indicate that an intravenous infusion of exendin-(9-39) in older adolescents and adult human subjects with $K_{ATP}HI$ raises fasting blood glucose levels. In this study we will evaluate the effects of exendin-(9-39) on glucose requirements to maintain euglycemia in subjects who have failed medical therapy.

2.1. Specific Aim

To examine the effect of exendin-(9-39) on glucose requirements to maintain euglycemia in infants with congenital hyperinsulinism unresponsive to medical therapy.

Secondary Aim. To determine therapeutic plasma levels, plasma half-life and pharmacokinetics of exendin-(9-39) during an intravenous infusion.

Hypothesis: *In infants with hyperinsulinism unresponsive to medical therapy, antagonism of the GLP-1 receptor by exendin-(9-39) will result in decreased glucose requirements to maintain euglycemia, as a result of suppressed insulin and increased glucagon secretion.*

Rationale: Infants with congenital hyperinsulinism present with severe hypoglycemia shortly after birth. Approximately 50% of these infants are unresponsive to available medical therapy (diazoxide and octreotide) and require a pancreatectomy to ameliorate the hypoglycemia. Before surgery, the maintenance of euglycemia is dependent on high glucose infusion rates (up to 20-25 mg/Kg/min) by intravenous or central lines. This practice is frequently associated with severe complications including sepsis and fluid overload which in the presence of the characteristic myocardial hypertrophy seen in these patients puts them at high risk for heart failure. Based on published studies demonstrating that exendin-(9-39) reduces the glucose infusion rates required to maintain blood glucose levels at a target level in normal human subjects (79) and our preliminary data demonstrating the insulin suppressant effects of exendin-(9-39) in subjects with hyperinsulinism, we propose that by continuously infusing exendin-(9-39) we will be able to reduce the glucose infusion rates needed to maintain euglycemia in infants with congenital hyperinsulinism.

Primary outcome variable: glucose infusion rate during the last 2 hrs of infusion of exendin-(9-39).

Secondary outcome variables: plasma glucose 1 hr after initiation of infusion, insulin, and betahydroxybutyrate levels measured at different intervals during the study. Exendin-(9-39) plasma levels.

Safety variables: Primary safety endpoints will include all types of adverse experiences, in addition to laboratory safety tests (hematology, chemistry, and urinalysis). 12-lead electrocardiograms (ECGs), vital signs and physical examinations will also be recorded.

3. Study Design

3.1. General Design

This is an open label randomized, crossover study aim to examine the effects of the investigative peptide, exendin-(9-39) on a key feature of the phenotype of congenital hyperinsulinism: 1) increased glucose requirements to maintain euglycemia.

The proposed human studies will be facilitated by the support of the Clinical and Translational Research Center (CTRC) at The Children's Hospital of Philadelphia and by having access to the largest pool of patients with congenital hyperinsulinism in this country through the Hyperinsulinism Center at The Children's Hospital of Philadelphia.

3.2. Experimental Design

We will compare the glucose infusion rate (measured in mg/Kg/min) required to maintain euglycemia (defined as a blood glucose \geq 70 mg/dL) with a concomitant intravenous infusion of exendin-(9-39) and vehicle in infants with congenital hyperinsulinism unresponsive to medical therapy. Each subject, in random order, will be evaluated on two separate days for a total of 12-15 hours each day.

During the first 3 hours, glucose infusion rates will be titrated to keep blood glucose in the range of 70-90 mg/dL, then, the study treatment period will start. On one day with an infusion of vehicle (normal saline) rates of glucose infusion to maintain blood glucose in the 70-90 mg/dL range will be calculated. To help inform the pharmacokinetic-pharmacodynamic relationship, subjects who have been able to discontinue the dextrose infusion and who are not on supplemental dextrose infusion at the end of the study will continue to be monitored without additional dextrose infusion for up to 3 hours after the end of the study drug infusion, or until blood glucose is < 70 mg/dL (whichever comes first). On the other day, subjects will receive a continuous intravenous infusion of exendin-(9-39) and the glucose infusion rates to maintain blood glucose in the 70-90 mg/dL range will be calculated. Studies will be carried out in the neonatal intensive care unit or the inpatient CTRC unit at The Children's Hospital of Philadelphia.

3.3. Study Population

Subjects will be recruited from patients referred to the Hyperinsulinism Center at The Children's Hospital of Philadelphia, the largest center in the USA, with approximately 30 referrals/year of children with medically-unresponsive hyperinsulinism and an equal number of children with medically-responsive hyperinsulinism. Three hundred and sixty one pancreatectomies have been performed in children with congenital hyperinsulinism within the last 16 years at this center. We plan to enroll approximately 20 additional subjects, beyond the 9 subjects already enrolled up through Amendment 6, making a total number of approximately 30 subjects for about 27 evaluable subjects and to include at least some subjects with diffuse disease.

3.3.1. Inclusion and Exclusion Criteria

Inclusion Criteria:

- Confirmed diagnosis of congenital hyperinsulinism (based on clinical criteria: insulin, beta hydroxybutyrate, and/or free fatty acid plasma levels at the time of hypoglycemia, and/or glycemic response to glucagon at the time of hypoglycemia)
- Age: from birth to 12 months
- Failure to respond to diazoxide (defined as the failure to maintain blood glucose \geq 70 mg/dL without supraphysiologic rates of glucose infusion: > 4-5 mg/Kg/min)

Exclusion Criteria:

- Evidence of a medical condition that might alter results, including active infection, kidney failure, severe liver dysfunction, severe respiratory or cardiac failure
- Current therapy at the time of initiation of study procedures with medications that affect glucose metabolism, such as high dose glucocorticoids, β -agonists, glucagon, diazoxide and octreotide. Subjects will be eligible to participate 4 hrs after glucagon discontinuation, 24 hrs after the last dose of octreotide and 72 hours after last dose of diazoxide

- Subjects with suspected Beckwith-Wiedemann syndrome or other syndromic forms of congenital hyperinsulinism

3.4. Study Procedures

1. Test of immediate hypersensitivity. All subjects will have 5 ng of exendin-(9-39) (0.05µg/mL) administered intradermally as a test of immediate hypersensitivity prior to the study. The test of immediate hypersensitivity may be done the day prior or the morning of the study prior to the start of the infusion. A wheal and flare reaction in the 30 minutes following peptide injection will be considered a positive test and the study will be canceled.
2. Baseline liver and kidney function: Baseline laboratories for evaluation of liver and kidney function (ALT, AST, GGT, BUN, creatinine) will be obtained if the subject has not had these tests done within 72 hrs of the study.
3. Safety evaluations: heart rate, blood pressure, respiratory rate and temperature will be measured each day at baseline. Heart rate, blood pressure and respiratory rate will be monitored then hourly during the treatment periods. Temperature will be measured at baseline, hourly during the study, and at the conclusion of the infusion periods. The 12-lead ECG, as well as laboratory safety evaluations including CBC, urinalysis, liver and kidney function will be repeated at the end of the study. Any clinically significant abnormality would be repeated until values have returned to normal range/baseline.
4. Study run-in period: During the 3 hours of run-in period, blood glucose will be monitored every 30 min by heel stick using a bedside glucose meter (Nova StatStrip point-of-care glucose monitor, Nova Biomedical Corporation, Waltham, MA, USA). The dextrose infusion rate will be adjusted to maintain glucose in the range of 70-90 mg/dL. The study run-in period will be timed to start with a feeding in the morning and we will kept consistent between study days.
5. Blood glucose monitoring during the study and maintenance of euglycemia. Blood glucose will be monitored every 30 minutes during the study period by heel stick using a bedside glucose meter (Nova StatStrip point-of-care glucose monitor, Nova Biomedical Corporation, Waltham, MA, USA). Rate of intravenous dextrose infusion will be adjusted as needed to maintain target blood glucose range of 70-90 mg/dL as per standard of clinical practice. If blood glucose concentration is ≤ 70 mg/dL a second sample will be obtained immediately for confirmation. Correction of values below the target range will be confirmed by measuring a blood glucose 15 minutes after adjustments to the glucose infusion rate.
6. Feedings: Infants will be allowed to continue feedings by mouth or by nasogastric/gastrostomy tube. Feedings will be continued every 3 hours and the volumes offered will be maintained equal during the two 9 hr study

- periods. The volume taken with each feeding will be recorded. Only intravenous glucose will be adjusted to maintain euglycemia.
7. Randomization: The investigational drug services will assign the order of the studies by randomization. They will inform the PI, study coordinator, and CTSC.
 8. Intravenous infusion of exendin-(9-39) and vehicle. All subjects will receive an infusion of exendin-(9-39) and vehicle for 9 hours on two separate days and in random order. Exendin-(9-39) /vehicle will be infused intravenously over a period of 9 hours starting at approximately the same time \pm 90 minutes on each day. The starting dose of exendin-(9-39) will be 1000 pmol/kg/min (0.2 mg/kg/hr). The dose will be escalated as outlined below. The volume of saline to be infused will be calculated to match the volume rate of exendin-(9-39).
 9. Post-infusion follow-up for subjects who have been able to discontinue dextrose infusion. Subjects who have been able to discontinue the dextrose infusion and who are not on supplemental dextrose infusion at the end of the study will continue to be monitored without additional dextrose infusion for up to 3 hours after the end of the study drug infusion, or until blood glucose is $<$ 70 mg/dL (whichever comes first). In addition to blood glucose monitoring every 30 minutes and betahydroxybutyrate every 1 hr from a capillary sample, a venous sample will be drawn at the end of 3 hours (or when blood glucose $<$ 70 mg/dL, whichever comes first) for plasma insulin and glucose.
 10. Dose schemes.

Scheme #1 (completed as of date of Protocol Amendment 7): exendin-(9-39) infused for 12 hrs at a dose of 100 pmol/kg/min (0.02 mg/kg/hr).

Scheme #2 (completed as of date of Protocol Amendment 7): exendin-(9-39) infused for 12 hrs at a dose of 200 pmol/kg/min (0.04 mg/kg/hr).

Scheme #3 (completed as of date of Protocol Amendment 7): exendin-(9-39) infused for 6 hrs at a dose of 500 pmol/kg/min (0.1 mg/kg/hr).

Scheme #4 (new as of date of Protocol Amendment 7): Dose escalation will be done as described below:

 - a. Cohorts 1-2: at least 3 and up to 6 subjects per cohort, will be included in each of the first two cohorts. In any of the first 2 cohorts, if discontinuation of intravenous dextrose is achieved in 2 out of the 3 subjects up to three additional patients (at least 2 with diffuse disease, as defined by PET scan and/or genetics) may be enrolled in order to meet the Success Stopping Criteria (see 11a below).
 - b. Cohorts 3- 4: four subjects, with at least 2 subjects with diffuse disease. If discontinuation of intravenous dextrose is achieved in 1 or 2 of the 4 subjects, an additional subject with diffuse may be enrolled in order to meet the Success Stopping Criteria (see 11a below).

- c. The dose will be increased in $\frac{1}{2}$ log increments between cohorts as specified below:

Group	Dose Scheme (mg/kg/hr for 9 hours)	Total Dose (mg/kg)	Number of Subjects
1	0.2	1.8	3-6
2	0.6	5.4	3-6
3	2	18	3-5
4	6	54	4-6

11. Stopping Criteria:

- a. Success Stopping Criteria: the dose escalation will be stopped if in a cohort at least 2 subjects with diffuse disease are able to have dextrose infusion discontinued for the final 2 hours of the study period.
- b. Safety Stopping Criteria: if an exaggerated pharmacology effect is observed (blood glucose greater than 200 mg/dL for 2 hours off dextrose infusion) dose escalation will be stopped and the dosing algorithm will be modified to proceed with a dose that is 2 fold higher the previous level observed to be safe. Dosing will be stopped if any severe adverse event is observed.

12. Calculation of glucose infusion rate. Glucose infusion rate over the last 2 hours of the treatment period will be calculated by adding the total amount of intravenous glucose (in mg) received over 2 hours divided by the weight in Kg and by time (120 min).

13. Determination of therapeutic plasma levels, plasma half-life and pharmacokinetics of exendin-(9-39). During the infusion with exendin-(9-39) blood samples will be obtained at 1, 5, and 9 hours, and at 1 and 3 hours after the infusion ends. Should there be difficulty in establishing blood drawing lines to obtain samples of the secondary outcome variables the study will proceed with collection of the primary outcome variable only (glucose infusion rate). Plasma levels of exendin-(9-39) will be determined by mass spectrometry.

14. Determination of plasma insulin, blood glucose, and betahydroxybutyrate levels: Venous samples for determination of plasma insulin and plasma glucose will be obtained at 0, 1, 5 and 9 hours during the study period. Betahydroxybutyrate will be obtained hourly by heel stick during the study period. For subjects in whom the dextrose infusion has been discontinued by the end of the study infusion betahydroxybutyrate will be obtained every hour until 3 hours post-dose (or when blood glucose \leq 70 mg/dL, whichever comes first). In these subjects an additional sample will be obtained at the end of 3 hours (or when blood glucose $<$ 70 mg/dL, whichever comes first) for plasma glucose and insulin. Should there be

difficulty in establishing peripheral blood drawing lines to obtain samples of the secondary outcome variables, (Insulin, exendin-(9-39) levels) the study will proceed with collection of the primary outcome variable only (glucose infusion rate). Capillary and venous blood glucose will be measured using the Nova StatStrip point-of-care glucose monitor (Nova Biomedical Corporation, Waltham, MA, USA). Betahydroxybutyrate will be measured at the bedside using a ketone meter (PrecisionXtra, Abbott Laboratories). Blood samples for plasma glucose, insulin and betahydroxybutyrate levels will be sent to the hospital chemistry laboratory for processing.

3.5. Sample Size and Data Analysis.

The goal of this study is to find the intravenous dose of exendin-(9-39) (and the plasma concentration) that is necessary to completely abolish the need for exogenous glucose administration to maintain normal blood glucose in children with congenital hyperinsulinism. The sample size of three for each dosing regimen is a sample of convenience and not based on statistical considerations. However, we offer the following considerations based on our previous studies: for the first 9 subjects studied under this protocol the mean \pm standard deviation (SD) baseline glucose infusion rate (GIR) was 13.2 ± 4.8 mg/kg/min. Our hypothesis is that exendin-(9-39) will decrease the glucose infusion rate required to maintain blood glucose > 70 mg/dL. A paired test is called for to compare the two conditions – exendin-(9-39) and vehicle; however, since we do not actually know the SD of differences, our sample size calculation is based on the more conservative t-test for independent samples, and we use the SD of 4.8 as an estimate of the common SD; using a two group t-test with a 0.05 two-sided significance level.

Reduction in GIR	Sample size for 80% power	Sample size for 90% power
25%	34	45
50%	9	12
100%	3	4

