3.5.2. Variables and time points

Pharmacodynamics (Primary Variable): Glucose infusion rate during the last 2 hours (hours 7-9) of infusion of exendin-(9-39) *versus* vehicle is the primary pharmacodynamic variable of interest, although blood glucose measurements over time will be utilized in exploratory PK/PD analyses.

Pharmacokinetics (Primary Variables): The pharmacokinetic variables of interest include $AUC_{0-\infty}$, AUC_{0-t} , maximal concentration (C_{max}), time to maximal

concentration (T_{max}), concentration at end of infusion (C_{eoi}), steady state volume of distribution (V_{ss}), clearance (CL) and half-life ($t_{1/2}$) of exendin-(9-39). These will be derived through both non-compartmental and model-based methods.

Safety (Secondary Variables): Primary safety endpoints will include all types of adverse experiences, in addition to laboratory safety tests (hematology, chemistry, and urinalysis). 12-lead electrocardiograms (ECGs), vital signs and physical examinations will also be recorded.

Secondary Variables: Plasma insulin, blood glucose and betahydroxybutyrate levels.

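### The primary endpoint is a dextrose rate that staff set in an open-label trial with no common adjustment rule, so expectation can lower GIR on the exendin-(9-39) day

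*Combined protocol and SAP*

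**What the plan says.** Section 3.1 states: "This is an open label randomized, crossover study". Under Section 3.4 item 7, drug services assign the order of the two infusions, and then: "They will inform the PI, study coordinator, and CTSC". No section masks anyone.

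The primary variable (Section 3.5.2; calculation in Section 3.4 item 12) is the intravenous glucose delivered in hours 7-9 of the infusion, per kg and per minute, compared between exendin-(9-39) and vehicle. Item 5 says how that amount is set: "Rate of intravenous dextrose infusion will be adjusted as needed to maintain target blood glucose range of 70-90 mg/dL as per standard of clinical practice". It gives no step size, no trigger for weaning and no named decision-maker.

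Item 5 does bound the discretion. On monitoring: "Blood glucose will be monitored every 30 minutes during the study period by heel stick". Values at or below 70 mg/dL are confirmed by a second sample. On low values: "Correction of values below the target range will be confirmed by measuring a blood glucose 15 minutes after adjustments to the glucose infusion rate".

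Items 10 and 11a make cohort expansion and the success stop depend on whether dextrose could be discontinued. Item 11a states no glucose condition and no comparison with the vehicle day.

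**The concern.** GIR in the last two hours is the sum of decisions to lower, hold or raise dextrose. At a reading of 88 mg/dL, weaning on one day and holding on the other both comply with item 5. If those who decide know which infusion is running, expectation can pull the exendin-(9-39) day down or keep the vehicle day up.

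Randomising the order does not help, because this bias goes with treatment and not with period. The mixed model in Section 3.5.4 has treatment, period, carry-over and subject terms. Attained glucose appears only in separate outcome analyses and in exploratory PK/PD work. Nothing planned separates a drug effect from running glucose lower on the drug day.

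The lack of a rule can also work the other way. From the mean of 13.2 mg/kg/min, reaching zero by hour 7 needs an average fall of 13.2/14 = 0.94 mg/kg/min at each of the 14 half-hourly checks (7 h x 2). A slow habit could hide a responder.

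**Working it through.** **Inputs from the plan.** Baseline GIR 13.2, SD 4.8 mg/kg/min, two-sided 0.05 (Section 3.5); about 27 evaluable, of whom about 20 are new (Section 3.3); target band 70-90 mg/dL (Section 3.4 item 5).

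**Assumed.** Within-subject correlation (the plan says the SD of differences is unknown), size of the shift, glucose space, normality. A paired t-test stands in for the mixed model.

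**1. The plan's sample-size table.** n per group = 2(z_0.975 + z_power)² SD²/δ², with δ = 13.2 x reduction. For 25%, δ = 3.3: 2 x 7.849 x 23.04/10.89 = 33.2, so 34 (80% power); 2 x 10.507 x 23.04/10.89 = 44.5, so 45 (90%). For 50%: 9 and 12. For 100%: 3 and 3, against 3 and 4 stated. The noncentral-t version gives 35/10/4 and 46/13/5. The table is sound and not in dispute.

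**2. How far GIR can move inside the band.**
- Upper bound, uptake proportional to glucose: 75 rather than 85 mg/dL gives 13.2 x 10/85 = 1.55, about 1.6 mg/kg/min; 70 rather than 90 gives 13.2 x 20/90 = 2.9 (22% of 13.2).
- Drift from 90 to 70 over the last two hours only, glucose space 1.5-2.5 dL/kg: 20 x 1.5/120 = 0.25 to 20 x 2.5/120 = 0.42 mg/kg/min.

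**3. False-positive rate with no drug effect.** SD of differences = 4.8 x √(2(1-ρ)); noncentrality = b√N/SD of differences; two-sided t with N-1 degrees of freedom. For N = 27 and ρ = 0.5 the SD of differences is 4.8, so b = 1.0 gives √27/4.8 = 1.08 and b = 1.5 gives 1.62.

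| Shift b (mg/kg/min) | N=27, ρ=0 | N=27, ρ=0.5 | N=27, ρ=0.8 | N=20, ρ=0.5 |
|---|---|---|---|---|
| 0 | 5% | 5% | 5% | 5% |
| 0.33 | 5.7% | 6.4% | 8.5% | 6.0% |
| 1.0 | 11% | 18% | 38% | 14% |
| 1.5 | 20% | 35% | 70% | 26% |
| 2.9 | 57% | 86% | >99% | 73% |

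**4. Can the shift alone meet item 11a?** Take the chance that an infant's need is no larger than the shift: Φ((b-13.2)/4.8). For b = 2.9 this is 1.6% per infant. The chance of at least two such infants is under 0.1% in a cohort of 3, 0.4% in a cohort of 6, and about 1.3% over four cohorts at the table's maximum sizes (6, 6, 5, 6). For b = 5 it is 4.4% per infant and about 9% over the four cohorts. Counting every subject as having diffuse disease makes these figures generous.

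**5. Is masking to hour 9 workable?** In favour: drug services already hold the order (item 7), saline volume is matched to the drug's volume rate (item 8), and venous samples fall at 1, 5 and 9 h on both days, with draws unique to the drug day starting after the infusion ends (items 13 and 14; Schedule of Blood Drawing). Against: the drug is diluted in saline with 0.25% albumin (Section 1.2.2) while the vehicle is normal saline (Section 3.2). The blood schedule also gives 18.2 mL for one day against 9.4 mL for the other, and the drug-level samples point to the larger being the drug day.

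**The case against.** Open label is a declared choice for a Phase 1/2 dose-escalation study with cohorts of convenience. Dextrose is under feedback: a cut that is not warranted lowers glucose, and item 5 then requires confirmation and correction. Plasma insulin and betahydroxybutyrate are measured on both days, are not set by staff and are analysed. Run-in timing and offered feed volumes are matched. Two neonates at 500 pmol/kg/min showed no GIR effect (Section 1.4), so expectation does not always manufacture one. Item 7 names the investigator, coordinator and research unit, not the person at the pump; that bedside staff know the infusion is inferred from the open label.

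Much of this stands as a limit on size. It does not remove the point. The checks mainly guard the lower edge of the band; they do not fix where within 20 mg/dL the infant is held or how fast dextrose is weaned. The other markers can corroborate a result but do not enter the GIR comparison.

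Two stronger readings are not supported:
- A reader might infer that expectation alone can produce discontinued-dextrose successes. With entry need above 4-5 mg/kg/min (Section 3.3.1), baseline 13.2 ± 4.8 and item 5 followed, step 4 makes this rare.
- A reader might add a small difference at each of 14 checks (3.3/14 = 0.24) until it reaches the table's 25% row. That ignores feedback: under proportional uptake, going from 13.2 to 9.9 takes glucose from 90 to 67.5 mg/dL, outside the band.

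**Conclusion.** The point holds as a bias in the GIR comparison that compliant staff could introduce. A shift of 1.0 to 1.5 mg/kg/min lies within the upper bound for the band. With 27 subjects, no drug effect and correlation 0.5 it lifts the false-positive rate from 5% to about 18-35%. Over correlations 0 to 0.8 the ranges are 11-38% (shift 1.0) and 20-70% (shift 1.5). If the only effect is drift in the last two hours, the inflation is slight (about 6% for a shift of 0.33).

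The bias can influence cohort-expansion and success decisions but is unlikely to create successes by itself. These sizes rest on assumed shifts, correlation and proportional uptake, and on a baseline GIR from nine subjects in place of a vehicle-day value for hours 7-9. The documents do not show that any such shift has occurred.

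**What to change.** For the remaining subjects:

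1. Change Section 3.4 item 7 so that drug services do not disclose the order to the staff who adjust dextrose until after hour 9 of the second infusion. Supply both infusions covered, identically labelled and volume-matched, with emergency unmasking. Release the order afterwards for the escalation review in Section 5.4.
2. In item 5, replace the deference to usual clinical practice with one written dextrose-adjustment procedure of the site's own choosing, applied identically on both days. If masking proves impractical, this alone is the fallback.
3. Report mean blood glucose in hours 7-9 by infusion beside GIR. Any glucose-adjusted GIR comparison should be a sensitivity analysis only, because glucose is a post-treatment variable.

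The cost is a protocol amendment, concealment of the infusions and a short written procedure; no added subjects or visits, and no change in sample size. Limits: the albumin-containing drug must be made indistinguishable from saline, the larger drug-day draws at 1, 5 and 9 h must be handled so that they do not reveal the infusion, a large drug effect may unmask, and subjects already studied are not covered.
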